3.2.2. Secondary End Points

- **Safety**

- Frequency, duration, and severity of all SAEs, AESIs, and NOCIs through 12 months after last study drug dose

- **Immunogenicity**

- Serum VP1 specific (GI.1 and GII.4) IgA through 6 months after study drug dose measured by Meso Scale Discovery (MSD) assay by dose level
 - Geometric mean concentration (GMC) at Day 180
 - Geometric mean fold rise (GMFR) from Day 1 to Day 180
- Breastmilk VP1 specific (GI.1 and GII.4) IgA through 6 months after study drug dose measured by Meso Scale Discovery (MSD) by dose level
 - Geometric mean concentration (GMC) at Day 60 and Day 180
 - Geometric mean fold rise (GMFR) from Day 1 to Day 60 and from Day 1 to Day 180
- Serum VP1 specific (GI.1 and GII.4) IgG through 6 months after study drug dose measured by Meso Scale Discovery (MSD) assay by dose level
 - Geometric mean concentration (GMC) at Day 1, Day 8, Day 29, and Day 180
 - Geometric mean fold rise (GMFR) from Day 1 to Day 8, from Day 1 to Day 29, and from Day 1 to Day 180
- Serum Blocking titers 50 (BT50) (GI.1 and GII.4) through 6 months after study drug dose measured by Histo-blood group antigen (HBGA) assay by dose level
 - Geometric mean titer (GMT) at Day 1, Day 8, Day 29, and Day 180
 - Geometric mean fold rise (GMFR) from Day 1 to Day 8, from Day 1 to Day 29, and from Day 1 to Day 180

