4.1. Overall Description of Trial Design

This is a multi-center, double-blind, randomized, placebo-controlled, single dose, dose ranging study in healthy, breastfeeding, female volunteers (≥ 18 years). The study will randomize 76 subjects and their breastfed infants aged >30 days to 11 months of age into three arms.

After reviewing and signing an informed consent, the subjects will undergo screening assessments to determine study eligibility up to a 45-day Screening Period.

On Day 1 of the randomized portion, subjects will be randomized in a 2:2:1 ratio to one of the three treatment arms to receive active vaccine at medium dose or high dose or placebo, as follows (Figure 1):

Figure 1

All subjects will be monitored for Solicited Symptoms of Reactogenicity (GI and systemic) for 1 week following the study drug dose and unsolicited AEs for 28 days post study drug dose (until Day 29) during the Active Period. Subjects will then enter the Follow-up period after Day 29 and will be monitored for specified unsolicited adverse events (SAEs, AESIs, and NOCIs) through Day 365 (Month 12) for safety and durability of immune response. Subjects will have samples (nasal, saliva, and serum) collected at the site, and will also self-collect samples (breastmilk and infant stool) at home for evaluation of immunogenicity as specified in the SoA (Table 1).

Table 2 Study Design

Treatment Group	Study Drug	Per Strain Dose (IU) +/- 0.5 log	Total Dose (IU/dose)	Dosing Schedule	No of Subjects
Arm 1 (n=30)	Bivalent GII.4/GI.1 vaccine	5×10^{10}	1×10^{11}	Day 1	30
Arm 2 (n=30)	Bivalent GII.4/GI.1 vaccine	1×10^{11}	2×10^{11}	Day 1	30
Arm 3 (n=16)	Placebo	N/A	N/A	Day 1	16
Total					76

Abbreviations: IU=infectious units

After vaccination on Day 1, the study will include an Active Study Period that runs through 4 weeks after administration (Day 29), and a Follow-up Period of one year for safety and duration of immune response. Study assessments will be conducted as shown in the SoA ([Table 1](#)). In addition, subjects will be contacted by phone between site visits to monitor for safety as specified in the SoA ([Table 1](#)).

A subject is considered to have completed the study if she completes the study active period at Day 29 (End of Study Active Period). Following completion of the Day 29 visit by all subjects the database will be cleaned and locked and the study unblinded. The Clinical Study Report (CSR) will be written based on the Day 29 dataset.

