8.1 Safety Assessment

The safety of the bivalent GI.1 and GII.4 vaccines will be evaluated through the reporting of Solicited Symptoms of Reactogenicity (GI and systemic) for 1 week following the study drug dose and through reporting of frequency, duration, and severity of unsolicited AEs for the next 28 days following the study drug dose. The subjects will then enter the Follow-Up Period after Day 29 and will be monitored for SAEs, AESIs, and NOCIs through Day 365 (Month 12) for safety and duration of immune response. Each SAE, AESI, and NOCI occurrence must be assessed for causality.

AESIs are listed in [Appendix 5](#), the occurrence of these events should be reported to the Sponsor in an expedited manner, similar to SAEs as described in [Section 9](#).

Planned time points for all safety assessments are provided in the SoA ([Table 1](#))

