9.4.2 Time Period and Frequency for Collecting AE, AESI, NOCIs, and SAE Information

All TEAEs, SAEs, AESIs, and NOCIs will be collected from the time of study drug dose until the follow up visit at the timepoints specified in the SoA ([Table 1](#)). TEAEs will be collected through Day 29. SAEs, AESIs, and NOCIs will be collected through Day 365.

Medical occurrences that begin before the start of study drug but after obtaining informed consent will be recorded as medical history/current medical conditions, not as AEs if they do not have a causal relationship with study participation. There are two situations to note as below:

- If the medical occurrence causes the subject to be excluded from the study, then it must be reported by the investigator. This event will then need to be classified as an "AE not related to the study drug."
- If the medical occurrence is the result of a protocol-specified intervention (prior to study drug dose), including but not limited to washout or discontinuation of usual therapy, diet, or a procedure then these must be reported appropriately as an AE (solicited and unsolicited), SAE, AESI, NOCI, and other reportable safety events by the Investigator.

All SAEs will be recorded and reported to the Sponsor or designee immediately and under no circumstance should this exceed 24 hours of being available. The Investigator will submit any updated SAE data to the Sponsor within 24 hours of it being available.

Investigators are not obligated to actively seek information on AEs or SAEs after conclusion of the study participation. However, if the Investigator learns of any SAE, including a death, at any time after a subject has been discharged from the study, and the Investigator considers the event to be reasonably related to the study drug or study participation, the Investigator must promptly notify the Sponsor.

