**Figure 1: Study Design**

After vaccination on Day 1, the study will include an Active Study Period that runs through 4 weeks after administration (Day 29), and a Follow-up Period of one-year post-dose for safety and duration of immune response. Study assessments will be conducted as shown in the SoA (Table 1). In addition, subjects will be contacted by phone between site visits to monitor for safety as specified in the SoA (Table 1).

A subject is considered to have completed the study if she completes the study active period at Day 29 (End of Study Active Period). Following completion of the Day 29 visit by all subjects the database will be cleaned and locked and the study unblinded, except the medical monitoring and pharmacovigilance team including anyone at the Sponsor, CRO and sites(s). The Topline Clinical Study Report (CSR) will be written based on the Day 29 clean datasets.

A subject is considered to have completed the Follow-up Period if she remains in the study through Day 365 (Month 12). Following completion of the Day 365 tele-health appointment for all subjects, the safety database will be cleaned and locked, and data collected during the Follow-up Period will be included in a CSR addendum.

All subjects will be monitored for Solicited Symptoms of Reactogenicity (GI and systemic) for 1 week following the study drug dose (until Day 8 (+2 days) scheduled site visit) and unsolicited AEs for 28 days post study drug dose (until Day 29 scheduled site visit) during the active period. Subjects will then enter the Follow-up period after Day 29 and will be monitored for specified unsolicited adverse events (SAEs, AESIs, and NOCIs) through Day 365 (Month 12) for safety and durability of immune response. Subjects will provide samples (nasal, saliva, serum, breast milk, and infant stool for evaluation of immunogenicity as specified in the Schedule of Activities (SoA) (Table 1).

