### **5.1.1 Subject Disposition**

Subject disposition will include the number of subjects who completed the study active period and treatment as planned, subjects withdrawn from the study active period and treatment, as well as the primary reason for early termination.

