14.3.3.1.4	Summary of Overall Unsolicited Treatment Emergent Adverse Events by Treatment arm, from Day 1 to Day 29 Post-Vaccination.	Safety
14.3.3.1.5	Summary of duration (in days) of Overall Unsolicited Treatment Emergent Adverse Events by Treatment arm, from Day 1 to Day 29 Post-Vaccination	Safety
14.3.3.1.6.1	Summary of Unsolicited Treatment Emergent Adverse Events by System Organ Class, Preferred Term and Treatment arm, from Day 1 to Day 29 Post-Vaccination	Safety
14.3.3.1.6.2	Summary of Unsolicited Treatment Emergent Adverse Events by System Organ Class, Preferred Term, Severity and Treatment arm, from Day 1 to Day 29 Post-Vaccination	Safety

Table Number	Table Title	Population
14.3.3.1.6.3	Summary of Unsolicited Treatment Emergent Adverse Events by System Organ Class, Preferred Term, Relationship and Treatment arm, from Day 1 to Day 29 Post-Vaccination	Safety
14.3.3.1.7.1	Summary of Serious Adverse Events by System Organ Class, Preferred Term and Treatment arm, from Day 1 to Day 29 Post-Vaccination	Safety
14.3.3.1.7.2	Summary of Serious Adverse Events by System Organ Class, Preferred Term, Severity and Treatment arm, from Day 1 to Day 29 Post-Vaccination	Safety
14.3.3.1.7.3	Summary of Serious Adverse Events by System Organ Class, Preferred Term, Relationship and Treatment Arm, from Day 1 to Day 29 Post-Vaccination	Safety
14.3.3.1.7.4	Summary of Serious Adverse Events by System Organ Class, Preferred Term and Treatment Arm, From Day 30 to Day 365 Post-Vaccination	Safety
14.3.3.1.7.5	Summary of Serious Adverse Events by System Organ Class, Preferred Term, Severity and Treatment Arm, from Day 30 to Day 365 Post-Vaccination	Safety
14.3.3.1.7.6	Summary of Serious Adverse Events by System Organ Class, Preferred Term, Relationship and Treatment Arm, from Day 30 to Day 365 Post-Vaccination	Safety
14.3.3.1.8.1	Summary of New Onset of Chronic Illness by System Organ Class, Preferred Term and Treatment arm, from Day 1 to Day 29 Post-Vaccination	Safety
14.3.3.1.8.2	Summary of New Onset of Chronic Illness by System Organ Class, Preferred Term, Severity and Treatment arm, from Day 1 to Day 29 Post-Vaccination	Safety
14.3.3.1.8.3	Summary of New Onset of Chronic Illness by System Organ Class, Preferred Term, Relationship and Treatment Arm, from Day 1 to Day 29 Post-Vaccination	Safety
14.3.3.1.8.4	Summary of New Onset of Chronic Illness by System Organ Class, Preferred Term and Treatment Arm, from Day 30 to Day 365 Post-Vaccination	Safety

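### The 12-month SAE, AESI and NOCI endpoint has no Day 1-365 table, follow-up loss is listed but not summarised, and protocol and SAP differ on who stays blinded after Day 29

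*SAP*

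**What the plan says.** **Endpoint and collection.** Protocol 3.2.2, repeated in SAP 2.3.2, defines the secondary safety endpoint as "Frequency, duration, and severity of all SAEs, AESIs, and NOCIs through 12 months after last study drug dose". Protocol 9.4.2 matches it: "SAEs, AESIs, and NOCIs will be collected through Day 365".

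**Tables.** SAP section 18 has one set of tables for the active period, for example "Summary of Serious Adverse Events by System Organ Class, Preferred Term and Treatment arm, from Day 1 to Day 29 Post-Vaccination", and a parallel set for follow-up, for example "Summary of Serious Adverse Events by System Organ Class, Preferred Term and Treatment Arm, From Day 30 to Day 365 Post-Vaccination". NOCIs and AESIs follow the same pattern. SAP 13.3, 13.4 and 13.5 announce summaries at Day 365 by SOC and PT, by severity and by relationship, but do not say on which day the window opens.

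**Disposition.** SAP 5.1.1 states: "Subject disposition will include the number of subjects who completed the study active period and treatment as planned", with withdrawals and the main reason for early termination. Disposition for Day 30-365 is Listing 16.2.1.2.2.

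**Blinding after Day 29.** Protocol 4.1, and 4.4 in nearly the same words, states: "Following completion of the Day 29 visit by all subjects the database will be cleaned and locked and the study unblinded". SAP 2.1, and again SAP 16, has "the study unblinded, except the medical monitoring and pharmacovigilance team including anyone at the Sponsor, CRO and sites(s". Protocol 8.1 requires: "Each SAE, AESI, and NOCI occurrence must be assessed for causality".

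**The concern.** The natural reading of the endpoint is the number of women in each arm with at least one such event between dosing and month 12. No listed table gives that number, and it cannot be obtained by adding the two windows.

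The late percentages would also appear without a summary of how many women were still being followed. Nothing in the planned tables would show whether a low late event rate reflects few events or few women observed.

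Finally, most late contacts are phone calls (Days 120, 240, 300 and 365; Days 60 and 180 are site visits). Reporting of AESIs and NOCIs, and judgement of their causality, can shift once the assignment is known. Protocol 11.1 says the placebo arm is there for the safety comparison, so this is the comparison that would suffer.

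**Working it through.** **1. Tables by window.** The relevant tables are 14.3.3.1.7.1 to 7.6 (SAEs), 8.1 to 8.6 (NOCIs) and 9.1 to 9.6 (AESIs).

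| Window | SAE | NOCI | AESI | Total |
|---|---|---|---|---|
| Day 1-29 | 3 | 3 | 3 | 9 |
| Day 30-365 | 3 | 3 | 3 | 9 |
| Day 1-365 | 0 | 0 | 0 | 0 |

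Together the two sets cover every day, so no period is left out. Event counts can be added across windows. Counts of women cannot.

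**2. What the two sets determine.** Let a be the women with an event in Day 1-29, b those with an event in Day 30-365, and n the arm size. The number with an event through Day 365 lies between max(a, b), when the smaller group lies wholly inside the larger, and min(a + b, n), when no woman has events in both. The documents give no expected event rate, so the counts below are assumptions.

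| n | a | b | Lower | Upper |
|---|---|---|---|---|
| 30 (one vaccine arm) | 2 | 3 | 3/30 = 10.0% | 5/30 = 16.7% |
| 30 (one vaccine arm) | 1 | 1 | 1/30 = 3.3% | 2/30 = 6.7% |
| 60 (both vaccine arms) | 2 | 4 | 4/60 = 6.7% | 6/60 = 10.0% |
| 16 (placebo) | 1 | 1 | 1/16 = 6.3% | 2/16 = 12.5% |

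If a or b is zero, the two limits coincide and nothing is lost.

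**3. Disposition.** SAP 5.1.1 describes completion of, and withdrawal from, the active period. Table 14.1.1 has no window in its title, so its content for Day 30-365 is not stated. The only output that names that window is the by-subject listing.

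**4. Blinding texts side by side.**

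| Place | Who stays blinded after the Day 29 lock |
|---|---|
| Protocol 4.1, 4.4 | No one is named |
| Protocol 6.7.2 | Subjects, investigators, site personnel and most of the sponsor are blinded; no end date is given |
| SAP 2.1, 16 | Medical monitoring and pharmacovigilance staff at sponsor, CRO and sites; participants are not mentioned, and investigators who report and judge events are not clearly included |

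**5. Largest possible unblinded share.** For the last woman enrolled, if unblinding fell on her Day 29, the share of post-dose days is (365 - 29)/(365 - 1) = 336/364 = 92.3%. Data cleaning and lock come first, so the true share is smaller for her. For women enrolled earlier it is smaller again.

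**The case against.** The strongest reply is that the material for the 12-month result is all there. Events are collected to Day 365, a final analysis and a CSR addendum follow (SAP 16), and by-subject listings cover both windows. With 76 women, counting each one once is feasible. SAP 13.3 to 13.5 can be read as promising the cumulative summary, which would leave only a mismatch with the table titles. The study is descriptive, with no hypothesis test (SAP 3.3). This limits the consequence, but a named secondary endpoint should have its own table and should not depend on reconstruction or on one reading of an ambiguous sentence.

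Four stronger readings are tempting, and the documents do not support them.

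- A reader might infer that 12-month safety is cut off at Day 29. It is not: collection, tables, listings and a final analysis run to Day 365, and completion of follow-up has its own Day 365 definition in Protocol 4.1 and 4.4.
- A reader might infer that the events are tabulated only from Day 30. The Day 1-29 tables stand directly above.
- A reader might infer that women lost to follow-up are counted as event-free. SAP 3.1 bases percentages on subjects with non-missing data and does not say how that applies to a woman lost before Day 365, so the treatment is unclear.
- A reader might attach confidence limits to the late percentages. SAP 13.3 to 13.5 plan only numbers, proportions and event counts.

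On blinding, the SAP exception mentions the sites and may be meant to reach site safety staff. The SAP also cites a protocol clarification memorandum of 24 January 2024 that is not among the documents and might settle the matter. As the texts stand, the protocol and SAP do not agree.

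**Conclusion.** The point holds in three parts.

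- The proportion of women with an SAE, AESI or NOCI through 12 months is not tabulated as the endpoint defines it. The planned tables give a range, whose width depends on how many women have events in both windows. The worked ranges rest on assumed counts.
- The SAP commits to no summary of follow-up completion or loss to set beside the late percentages. No loss rate is given in the documents, so the size of any distortion cannot be stated.
- Protocol and SAP differ on who stays blinded after the Day 29 lock, while reporting and causality assessment continue to Day 365. The 92% figure is an upper bound for one woman.

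For a descriptive Phase 1 study with full listings this is of moderate weight. It should be corrected because the remedy is simple and the result is a named endpoint.

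**What to change.** 1. Add Day 1-365 tables for SAEs, AESIs and NOCIs by SOC and PT, by severity and by relationship, each woman counted once, and designate them as the output for the secondary endpoint. Keep the two window sets as support.
2. Add Day 365 follow-up completion and reasons for loss, by arm, to the disposition summary, and show person-time of follow-up beside the late event counts. Changing the denominator to women who entered follow-up would not be enough, because it does not correct for loss after entry.
3. Reconcile Protocol 4.1 and 4.4 with SAP 2.1 and 16 so that participants and the site staff who collect or judge events stay blinded to individual assignment until the Day 365 lock. Only a named analysis team would be unblinded at Day 29, and emergency unblinding would stay as it is.

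Cost: nine further tables (three event types by three breakdowns), a disposition summary and a person-time column, all from data already collected. The protocol change is short but needs prospective ethics approval under Protocol 12.2. By-subject assignments would be withheld from sites until the Day 365 lock.

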**19. LISTINGS**

Listing Number	Listing Title	Population
16.2.1	Subject Disposition	
16.2.1.1	Analysis Populations by Treatment arm	ScS
16.2.1.2.1	Subject Disposition by Treatment arm from Day 1 to Day 29	ITT
16.2.1.2.2	Subject Disposition by Treatment arm from Day 30 to Day 365	ITT
16.2.2	Protocol Deviations	
16.2.2.1	Protocol Deviations by Treatment arm	ITT
16.2.4	Demographic and Other Baseline Data	
16.2.4.1	Demographics and Baseline Characteristics by Treatment arm	Safety
16.2.4.1.a	Demographics and Baseline Characteristics (Infant) by Treatment arm	Safety
16.2.4.2	Medical/Surgical History	Safety
16.2.4.2.a	Vaccination Status	Safety
16.2.4.2.b	Infant Health	Safety
16.2.4.3	Urine Drug Screen	Safety
16.2.4.4	Alcohol Test	Safety
16.2.4.5	Serology	Safety
16.2.4.6.1	Eligibility Criteria	ScS
16.2.4.6.2	Screen Failure Subjects	ScS
16.2.5	Treatment Administration	
16.2.5.1	Subject Randomization by Treatment arm	ITT
16.2.5.2	Study Drug Administration by Treatment arm	ITT
16.2.6	Immunogenicity	
16.2.6.1	Serum VP1 Specific GI.1 IgA (AU/mL) Concentration by Treatment Arm	Immunogenicity
16.2.6.2	Serum VP1 Specific GII.4 IgA (AU/mL) Concentration by Treatment Arm	Immunogenicity
16.2.6.3	Breast Milk VP1 Specific GI.1 IgA (RLU/ug of total IgA) Concentration by Treatment Arm	Immunogenicity
16.2.6.4	Breast Milk VP1 Specific GII.4 IgA (RLU/ug of total IgA) Concentration by Treatment Arm	Immunogenicity
16.2.6.5	Serum VP1 Specific GI.1 IgG (AU/mL) Concentration by Treatment Arm	Immunogenicity
16.2.6.6	Serum VP1 Specific GII.4 IgG (AU/mL) Concentration by Treatment Arm	Immunogenicity
16.2.6.7	Serum GI.1 Blocking Titers 50 (BT50) by Treatment Arm	Immunogenicity

[figure not shown]
Listing Number	Listing Title	Population
16.2.6.8	Serum GII.4 Blocking Titers 50 (BT50) by Treatment Arm	Immunogenicity
16.2.7	Adverse Events	
16.2.7.1	Solicited Symptoms reported between Day 1 to Day 8, by Treatment Arm	Safety
16.2.7.2	Solicited Symptoms Diary Card with Severity Grading, by Treatment Arm	Safety
16.2.7.3	Unsolicited Adverse Events reported between Day 1 to Day 29, by Treatment Arm	Safety
16.2.7.4.1	Serious Adverse Events reported between Day 1 to Day 29, by Treatment Arm	Safety
16.2.7.4.2	Serious Adverse Events reported between Day 30 to Day 365, by Treatment Arm	Safety
16.2.7.5.1	Adverse Event of New Onset Chronic Illness reported between Day 1 to Day 29, by Treatment Arm	Safety
16.2.7.5.2	Adverse Event of New Onset Chronic Illness reported between Day 30 to Day 365, by Treatment Arm	Safety
16.2.7.6.1	Adverse Event of Special Interest reported between Day 1 to Day 29, by Treatment Arm	Safety
16.2.7.6.2	Adverse Event of Special Interest reported between Day 30 to Day 365, by Treatment Arm	Safety
16.2.7.7.1	Unsolicited TEAEs related to study drug Day 1 through Day 29, by Treatment Arm	Safety
16.2.7.8.1	Death event reported between Day 1 to Day 29, by Treatment Arm	Safety
16.2.7.8.2	Death event reported between Day 30 to Day 365, by Treatment Arm	Safety
16.2.8	Other Safety	
16.2.8.1	Vital Signs by Treatment arm	Safety
16.2.8.2	Physical Examination by Treatment arm	Safety
16.2.8.3	Pregnancy Test Results by Treatment arm	Safety
16.2.9	Prior & Concomitant Medication	
16.2.9.1	Prior Medication by Treatment arm	Safety
16.2.9.2	Concomitant Medication by Treatment arm	Safety
16.2.9.3	Surgical and Medical Procedure	Safety
16.2.9.3.a	Surgical and Medical Procedure (Infant)	Safety

**20. FIGURES**

Figure Number	Figure Title	Population
14.2	Immunogenicity	
14.2.1.1	Serum VP1 specific GI.1 IgA Geometric Mean Concentration Bar Plot Over Time by Treatment Arm, between Day 1 to Day 29	Immunogenicity
14.2.1.2	Serum VP1 specific GI.1 IgA Geometric Mean Concentration Bar Plot Over Time by Treatment Arm, between Day 1 to Day 180	Immunogenicity
14.2.2.1	Serum VP1 specific GII.4 IgA Geometric Mean Concentration Bar Plot, by Treatment Arm, between Day 1 to Day 29	Immunogenicity
14.2.2.2	Serum VP1 specific GII.4 IgA Geometric Mean Concentration Bar Plot, by Treatment Arm, between Day 1 to Day 180	Immunogenicity
14.2.3.1	Breast Milk VP1 specific GI.1 IgA Geometric Mean Concentration Bar Plot Over Time by Treatment Arm, between Day 1 to Day 29	Immunogenicity
14.2.3.2	Breast Milk VP1 specific GI.1 IgA Geometric Mean Concentration Bar Plot Over Time by Treatment Arm, between Day 1 to Day 180	Immunogenicity
14.2.4.1	Breast Milk VPI specific GII.4 IgA Geometric Mean Concentration Bar Plot, by Treatment Arm, between Day 1 to Day 29	Immunogenicity
14.2.4.2	Breast Milk VPI specific GII.4 IgA Geometric Mean Concentration Bar Plot, by Treatment Arm, between Day 1 to Day 180	Immunogenicity
14.2.5.1	Serum VP1 specific GI.1 IgG Geometric Mean Concentration Bar Plot, by Treatment Arm, between Day 1 to Day 29	Immunogenicity
14.2.5.2	Serum VP1 specific GI.1 IgG Geometric Mean Concentration Bar Plot, by Treatment Arm, between Day 1 to Day 180	Immunogenicity
14.2.6.1	Serum VP1 specific GII.4 IgG Geometric Mean Concentration Bar Plot, by Treatment Arm, between Day 1 to Day 29	Immunogenicity
14.2.6.2	Serum VP1 specific GII.4 IgG Geometric Mean Concentration Bar Plot, by Treatment Arm, between Day 1 to Day 180	Immunogenicity
14.2.7.1	Serum Blocking Titers 50 (BT50) GI.1 IgG Geometric Mean Titer Bar Plot, by Treatment Arm, between Day 1 to Day 29	Immunogenicity
14.2.8.1	Serum Blocking Titers 50 (BT50) GII.4 IgG Geometric Mean Titer Bar Plot Over Time by Treatment Arm, between Day 1 to Day 29	Immunogenicity

